[name], MSPH Professor of Internal Medicine Cardiovascular Genetics Research [name] Office:

[name], MS
Consultant
Department of Radiology
Division of Neuroradiology
Professor of Radiology
Direct:

Secretary [contact] [contact] [contact]

[name], FACP Assistant Professor of Medicine Women's Health Clinic (Division of General Internal Medicine) Division of Endocrinology, Metabolism and Nutrition

[name]
Clinical Research Coordinator
Radiology Research

[name] Health Science Research – Biomedical Harwick 7

[name]

[name] Radiology - Nuclear Medicine

[name]

[name], DrPH
Chief, Division of Preventive Medicine
Brigham and Women's Hospital
Professor of Medicine and the
Michael and Lee Bell Professor of
Women's Health
Harvard Medical School
[name]
[name]

[name] Surgical Research

[name]

[name], MS. FACOG, FRCOG (UK)

Professor, Interim Section Chief, Division of Reproductive Endocrinology & Infertility Fellowship Director, Reproductive Endocrinology & Infertility Director, Yale REI Program for Polycystic Ovarian Syndrome Director, Yale REI Menopause Program Associate Chair for Education Department of Obstetrics, Gynecology &

Reproductive Sciences Yale School of Medicine. [name].

[name]

[name] Medical Imaging Opus 2 – 163

[name]

[name] Medical Imaging Analyst Opus 2 – 147

PRÉCIS

Study Title

Prevention of Alzheimer's Disease in Women: Risks and Benefits of Hormone Therapy - Continuation of "The Kronos Early Estrogen Prevention Study (KEEPS)"

Objectives

The objectives are to assess the long-term risks and benefits of menopausal hormone therapy (mHT) on Alzheimer's disease (AD) pathophysiology, cerebrovascular, cognitive, and mood health in women treated with transdermal 17β-estradiol (tE2) or oCEE compared to placebo within three years of menopause, which is considered to be the "critical window" for mHT.

Design, Outcomes, Interventions, and Duration

This project is proposed as a continuation to the Kronos Early Estrogen Prevention Study (KEEPS), a nationwide, multi-center, randomized blinded study of mHT in recently menopausal women.

The current investigation will include assessments conducted over 3-4 visits, consisting of chemistries, questionnaires, neurocognitive testing, and brain imaging.

Interventions and Duration

- interventions and Buration
 - Explanation of the study and confirmation of eligibility
 - Measurement of height, weight, waist and hip circumference, blood pressure
 - and pulse
 - Review of medical history
 - o Blood tests
 - Questionnaires about general health and well-being, COVID-19 questionnaire quality of life, sleep, emotional health and mood and pregnancy history.
 - Neurocognitive tests
 - Brain magnetic resonance imaging (MRI)
 - Brain positron emission tomography (PET): F-18 Florbetapir PET (all sites) and F-18 AV-1451 PET (only at the Mayo Clinic & BAI site)
 - All tests and procedures will take about 9 hours total to complete.

Participants will be on study until all of the following are completed: medical assessment, questionnaires, blood work, neurocognitive studies, , brain MRI, brain PET.

Sample Size and Population

Our targeted enrollment is 492 (n=83 at the Mayo Clinic) participants across eight sites; 13 years post-randomization (4 years of study drug and 9 years after the end of study drugs).

Women who enrolled in the KEEPS study at 8 sites will be invited to participate (total n=688; Mayo Clinic n=118). In order to reduce the costs but retain as many participants as possible, we merged the cohorts in two sites by taking advantage of the proximity of geographic location. Columbia University will be recruiting the Einstein Montefiore Center's participants; therefore 7 sites including Mayo Clinic Rochester will be participating.

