4. SELECTION AND ENROLLMENT OF PARTICIPANTS

This proposal is developed as a continuation of the Kronos Early Estrogen Prevention Study (KEEPS; NCT00154180; Mayo Clinic IRB #2241-04-00).

This study will involve a single follow-up evaluation of brain imaging and cognitive function of all women who were randomized to mHT or placebo, approximately 13 years post-randomization and nine years after the end of mHT administration phase in KEEPS. All women who were enrolled in KEEPS in the eight sites will be invited to participate. Names and contact information of the participants were retained by site PIs.

Table 1. Study timeline and enrollment plan and assuming 70% participation rate

Site	Year 1		Year 2	Year 3	Year 4	Year 5	Total
Brigham & Women's	Preparation phase		21	21	15	Analysis	57
Columbia & Einstein	Preparation		42	42	30	Analysis	142
Mayo Clinic	Preparation phase		30	30	22	Analysis	83
University of San Francisco	Preparation phase		6	19	14	Analysis	39
University of Utah	Preparation phase		24	24	16	Analysis	64
Banner Alzheimer's Institute	Preparation phase		7	23	16	Analysis	46
Yale University Preparation 1		10	20	20	11	Analysis	51
Total		38	150	179	125		492

Each woman will be invited to participate by a letter from the study coordinator at each site. For those women expressing interest, the study coordinator will provide a detailed description of the study and those who are willing to participate will be scheduled for study visits at 13-year post-randomization landmark. Information on current use of medications and interim cardiovascular, cerebrovascular, or neurologic disease events will be collected during the clinical visit. Study participants will be scheduled to complete all assessments and tests over three or four visits. Study data will be de-identified and transferred to the Mayo Clinic and UW through secure file transfer protocols. Data will be stored at each institution's data center.

For participants that have moved away from the site in which they originally were enrolled, may participate at one of the participating sites listed that is closest to their new address. Once they have responded that they are willing to participate at a different site, contact information will be given to the new enrolling site in order to communicate with the participant for Consenting, Enrollment and Scheduling Visits.

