At Mayo Clinic, 118 women met the inclusion criteria for randomization into the KEEPS trial. This study will recruit these 118 menopausal women for follow-up. Assuming a 70% retention rate, we project that our cohort will consist of approximately 82 subjects.

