
these standard deviations as estimates of variability in our projected sample, we estimated the minimum detectable effect sizes in the pairwise comparisons (using Cohen's d) with 80% power.

Table 3. Minimum detectable effect sizes for projected sample size and 80% power.

Comparison	All	APOE ε4 non-carriers	APOE ε4 carriers
oCEE vs. Placebo	0.308	0.358	0.619
tE2 vs. Placebo	0.312	0.355	0.665

These effect sizes fall in the medium (all and $APOE\ \epsilon 4$ non-carriers) to large ($APOE\ \epsilon 4$ carriers) range. In our 84 month KEEPS data, most of our observed Cohen's d values were close to 0.34 (all subjects), 0.37 ($APOE\ \epsilon 4$ non-carriers), and 1.18 ($APOE\ \epsilon 4$ carriers). We anticipate the effect sizes to be at least this large in the KEEPS Continuation study. Since the minimum detectable effect sizes in **Table 3** are close to or smaller than these values, we anticipate having adequate power to detect pairwise differences. We would expect similar effect sizes for the other outcomes.

9.3 Primary Objective 2

To determine the differences in longitudinal changes in cognitive performance and mood in postmenopausal women who were treated with one of the two mHTs vs. placebo.

Primary Hypothesis 2: Performance on four cognitive factors described in our bi-factor model and on POMS mood indices are different in women who were treated with tE2 vs. placebo and oCEE vs. placebo.

Hypothesis 2a: Cognitive and mood differences in women who were treated with tE2 vs. placebo and oCEE vs. placebo are modified by *APOE*e4 status (carrier/noncarrier).

Hypothesis 2b: Cognitive and mood differences in women who were treated with tE2 vs. placebo and oCEE vs. placebo are modified by the vascular disease risk at 13 years post-randomization.

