Power for Objective 2: Power and sample size estimates to detect significant changes in cognitive function are based on Mayo Clinic pilot data collected over five unequally-spaced observation time points (0,18, 36, 48, and 84 months) with the verbal learning and memory factor as the longitudinal outcome and treatment groups vs. placebo as predictors. We assumed normally distributed continuous outcomes with missing data, two predictors (oCEE and tE2) with regression coefficients in factor score units for rate of change of, respectively, -0.20 and -0.11; a variance of 2.09 for the random intercept, a variance of 0.03 for the random slope, and a correlation between random slope and random intercept terms set to 0.07. Using a two-tailed α =0.05, a total sample size of 492 individuals will achieve a power of 82% to reject the hypothesis for this aim.

Alternative Strategy: We will evaluate our participants for incident MCI and dementia, but we do not expect to have sufficient power to test the differential progression to MCI or dementia in each of the mHT vs. placebo groups. However, we will explore this alternative approach if we have a sufficient number of incident cases.

9.4 Primary Objective 3

To determine the associations between imaging biomarkers investigated in Aim 1, and longitudinal changes in cognitive performance and mood investigated in Aim 2.

Primary Hypothesis 3: Higher Aβ (primary outcome), AV-1451 and WMH load, and smaller regional cortical thickness are associated with a longitudinal decline in cognitive performance since randomization

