Statistical Analysis for Objective 3: Repeated cognition and mood measures will be available for time points ranging from trial baseline to 13 years post-baseline; we will use the same cognitive factor scores and POMS as in Aim 2. For each measure in Aim 2, we will consider the values at year 13, the changes in values from baseline to year 13, and predicted annual changes in values at year 13 (slopes). Aβ PET SUVR, WMH, and AD signature thickness and hippocampal volume will only be available at 13 years post-baseline. We will use plots and Pearson or Spearman correlation coefficients, as appropriate given the distributions of the variables involved, to describe and measure associations between cognitive/mood measures and imaging biomarkers. As in the previous aims, we will explore and include site and covariate effects through regression models, transform variables as needed to meet assumptions, and perform sensitivity analyses with and without individuals who continued to use mHT after the mHT administration phase ended.

Power for Objective 3: With 492 individuals and α =0.05, we will have 80% power to detect Pearson correlation coefficients as small as 0.127. In a linear regression, this would be an increase in the model R² due to the association of interest as small as 0.016. We should thus have sufficient power to detect small associations.

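### The recruitment target and power N of 492 does not follow from the plan's own 70% participation of 688 invited women, which gives 482; Table 1 contains the same gap of 10

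*Combined protocol and SAP*

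**What the plan says.** The Précis (Sample Size and Population) sets the target: "Our targeted enrollment is 492 (n=83 at the Mayo Clinic) participants across eight sites". It goes on to say that women enrolled in KEEPS at eight sites "will be invited to participate (total n=688; Mayo Clinic n=118").

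Section 4 confirms who is approached: "All women who were enrolled in KEEPS in the eight sites will be invited to participate". Table 1 in that section is captioned "Study timeline and enrollment plan and assuming 70% participation rate" and prints a grand total of 492. For Mayo, section 4 adds: "Assuming a 70% retention rate, we project that our cohort will consist of approximately 82 subjects".

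The same N of 492 carries the power statements. Section 9.3 says that "a total sample size of 492 individuals will achieve a power of 82" per cent. Section 9.4, also at N = 492, says "we will have 80% power to detect Pearson correlation coefficients as small as 0.127". Table 3 in section 9.2 refers only to a projected sample size and gives no number.

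**The concern.** Three figures are given for one head count: 688 invited, 70% taking part, 492 enrolled. The first two multiply to 482, so the third does not follow from them.

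Table 1 should show how the target is built up, but its two margins disagree by the same ten women. A reader cannot tell whether the plan expects 482 or 492 participants, or whether Yale is to recruit 51 or 61.

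The N matters because it is both the recruitment target and the sample size behind the Objective 2 and Objective 3 power. If 70% participation is achieved exactly, the study falls ten short of the N on which those statements rest.

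**Working it through.** **Inputs.** Invited 688 and target 492 (Précis); participation 70% (section 4, Table 1 caption); site and yearly entries (Table 1); two-sided α = 0.05 with 82% power (section 9.3); α = 0.05, r = 0.127 and 80% power (section 9.4).

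**Step 1: target against rate.**
- 0.70 × 688 = 481.6, so 482.
- 492 − 482 = 10, and 10/492 = 2.03%.
- Rate needed for 492: 492/688 = 71.5%.
- Invitations needed at 70%: 492/0.70 = 702.9, so 703.
- The full KEEPS enrolment of 727 at nine sites (section 3) does not give 492 either: 0.70 × 727 = 508.9.

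**Step 2: Table 1 margins.** The yearly totals reproduce the printed grand total: 38 + 150 + 179 + 125 = 492. The printed site totals do not: 57 + 142 + 83 + 39 + 64 + 46 + 51 = 482. The latter fits the invited number: 482/0.70 = 688.6.

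**Step 3: locating the gap.**

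| Site | Sum of legible cells | Printed total |
|---|---|---|
| Brigham & Women's | 21+21+15 = 57 | 57 |
| Columbia & Einstein | 42+42+30 = 114 (Year 1 cell not legible) | 142 |
| Mayo Clinic | 30+30+22 = 82 | 83 |
| San Francisco | 6+19+14 = 39 | 39 |
| Utah | 24+24+16 = 64 | 64 |
| Banner | 7+23+16 = 46 | 46 |
| Yale | 10+20+20+11 = 61 | 51 |

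The Columbia row implies a Year 1 cell of 142 − 114 = 28. With Yale's 10 this gives 38, the printed Year 1 total. So the yearly totals count Yale's Year 1 entry of 10, while Yale's row total does not (20 + 20 + 11 = 51). The Year 2 and Year 3 cells add to 150 and 179 as printed. The Year 4 cells add to 124 against 125. A Mayo Year 4 entry of 23 would settle both that and the Mayo row, and it has no bearing on the gap of 10.

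**Step 4: effect on power.**
- *Objective 3* (Fisher z): power = Φ(atanh(0.127) × √(N − 3) − 1.96). At N = 492, Φ(0.1277 × 22.11 − 1.96) = 80.6%. At N = 482, Φ(0.1277 × 21.89 − 1.96) = 79.8%.
- *Objective 2*: the 82% cannot be rebuilt, because section 9.3 gives no residual variance or missing-data rate. Treating it as a single-coefficient test and rescaling: 1.960 + 0.915 = 2.875, and Φ(2.875 × √(482/492) − 1.96) = 81.2%. This is indicative only.
- *Aim 1*, assuming three equal arms: detectable d = (1.960 + 0.842) × √(6/N), which is 0.309 at 492 and 0.313 at 482.

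**Step 5: which N do the other figures point to?** The evidence is mixed. The smallest r detectable with 80% power is tanh(2.802/√(N − 3)), which is 0.126 at 492 and 0.127 at 482, so the printed 0.127 fits 482. Table 3 prints d of 0.308 and 0.312. With equal arms these correspond to total N of 496 and 484, which bracket 492 and exclude 482. The documents give no arm sizes, so neither sign is decisive.

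**The case against.** The strongest objection is that the Table 1 evidence rests on damaged text. The Columbia Year 1 cell is missing, and the Yale label and the header are broken. A single misread digit in Yale's total, 61 read as 51, would bring the site totals to 492. The only grand total printed is 492; 482 is a sum that the documents nowhere state. This stands as a caution about the Yale row. It does not reach the main conflict, which is in plain text in the Précis and in section 4: with Yale at 61, the table would agree with itself and still exceed 70% of 688 by ten.

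A second objection is that 492 is a target and 70% a rounded planning figure, and that the pool could be wider than 688. Section 3 counts 727 women at nine sites, and the inclusion criteria ask only for participation in the original trial. However, the Précis and section 4 both limit invitations to the women of the eight sites, and the Précis puts their number at 688. Table 1 also applies the 70% to reach its totals. Site-level rounding explains Mayo's 82 against 83 (0.70 × 118 = 82.6), but not ten women.

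The third objection is that the consequence is negligible. This is right as to size, and it is why the point is minor. Objective 3 power still rounds to 80% at either N.

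**Conclusion.** The concern holds as a minor inconsistency. The figures 492, 688 and 70% cannot all stand as written, and the difference is 10 women, or 2.03% of N. It does not invalidate any power calculation: the loss is under one percentage point for Objective 3 (80.6% to 79.8%) and for Objective 2 (82% to about 81%, by rescaling).

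The conflict with the 70% rate needs no assumption beyond the stated figures. The placing of the gap in the Yale row depends on that row having been read correctly. The Aim 1 figures assume equal arms. Whether 482 or 492 is intended cannot be decided from the documents.

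**What to change.** 1. Check Table 1 against its source. Correct Yale's Year 1 entry or its row total, and settle the one-person discrepancy in the Mayo row and the Year 4 column.
2. State one N with its matching participation rate in the Précis, Table 1 and sections 9.3 and 9.4: either 482 at 70%, or 492 at 71.5%.
3. If 482 is adopted, re-run the Objective 2 power with its original inputs and give Objective 3 as r = 0.127 at N = 482. If 492 is kept, r = 0.127 can stand, since its power is slightly above 80%, and only the rate and the table entries change.

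It would help to name the N used for Table 3 at the same time.

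The cost is a few text and table corrections, plus one power re-run if 482 is chosen. No extra enrolment is needed, and neither the design nor the analysis changes.

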1. STUDY OBJECTIVES

1.1 Primary Objectives

To assess effects of menopausal hormone therapy and normal aging on cognitive performance and imaging markers of brain structure in women approximately thirteen years after enrolling in the KEEPS trial. KEEPS participants were randomized to oral or transdermal estrogen treatments or placebo within three years of menopause. This is a follow up study of these women approximately thirteen years after randomization (9 years after study completion.) **No treatments are given as part of this study**; any current hormonal treatments are by choice and prescribed by the participant's personal physician.

Aim 1: Determine the differences in $A\beta$ and tau pathology of AD, cerebrovascular lesions and brain structure in women who were treated with either oCEE or tE2 compared to placebo during early post menopause.

Hypothesis 1: Aβ, tau, cerebrovascular lesions and brain structure are different in women who were treated with tE2 vs. placebo and oCEE vs. placebo during early post menopause, modified by the APOE ε4 status.

Aim 2: Determine the differences in longitudinal changes in cognitive performance and mood in women who were treated with either oCEE or tE2 compared to placebo within three years of menopause.

Hypothesis 2: The longitudinal change in cognitive performance and mood over 13 years in women treated with one of the two active estrogen formulations (tE2 or oCEE) will differ from longitudinal cognitive and mood changes occurring in women who received placebo, modified by the *APOE* ε4 status.

Aim 3: To determine the association between imaging markers investigated in Aim 1 and the change in cognitive performance investigated in Aim 2 eight to nine years after completing KEEPS trial participation.

Hypothesis 3: Higher $A\beta$, tau and WMH load, and smaller regional brain volumes are associated with a longitudinal decline in cognitive performance and mood outcomes since randomization.

2. BACKGROUND AND RATIONALE

2.1 Alzheimer's disease represents a public health crisis, especially for women

Women represent approximately $\frac{2}{3}$ of the five million patients with AD dementia. At the age of 65, a woman's lifetime risk for AD is nearly double that for a man, 17.2% compared to 9.1%.1 While it remains imperative to develop effective AD treatments, the prevailing sentiment is that initiating treatment *after* the onset of clinical symptoms may be "too little, too late" to alter disease course, 2,3 necessitating a shift toward AD prevention in individuals who are at-risk. Thus, there is an urgent need for effective *prevention strategies* to address the suffering and untenable costs associated with AD. How menopausal hormone therapies (mHT) influence the risk of AD remains an area of controversy. As the number of postmenopausal women in the world is projected to be ~1.1 billion in less than a decade from today, 4 and that mHT is prescribed to relieve symptoms of menopause, it is critical that this controversy be addressed in rigorous manner. The results of the proposed research will address this controversy by applying principles of pharmacogenomics with state-of-the art imaging and cognitive testing in postmenopausal women whose hormonal usage and cardiovascular risk factors have been documented for over 10 years. The outcomes would provide evidence for a potential preventive

2.2 The KEEPS Continuation represents a singular opportunity

The KEEPS, and its ancillary KEEPS Cognitive and Affective Study (KEEPS-Cog) recruited women from 2005 to 2008; all participants were 6 to 36 months past their last menses (age=42-58). The goals of this randomized, double-blinded, placebo-controlled trial was to investigate the cardiovascular, cognitive, and mood effects of two forms of mHT (tE2 and oCEE) administered proximal to the menopausal transition to women whose cardiovascular risks were minimal.⁵ In the Women's Health Initiative (WHI) and its Memory Study (WHIMS), oCEE and medroxyprogesterone acetate initiated decades past the menopausal transition, increased the risk of dementia.⁶ Since the WHI, prescribing practices have changed such that there are a wide variety of mHTs used to alleviate menopausal symptoms. Whether alternative formulations of mHT, such as tE2 used in KEEPS, can preserve neuronal integrity and decrease the risk of dementia when administered early in menopause remains controversial.7-14 Our pilot data suggest possible differential effects for two mHT formulations. The inclusion of women who were at higher risk for cardiovascular disease and well past their menopausal transition were considered major design flaws of the WHI study¹⁵ and WHIMS, ^{16,17} respectively. The KEEPS and KEEPS-Cog were designed to address these limitations, and to determine whether lower doses and different formulations of mHT could reduce the risk of cognitive decline and mood changes that occur during menopausal transition, but only if initiated shortly after menopause during the "critical window"; that is, a time-point that would be consistent with a preventive strategy. 18 Women enrolled in the KEEPS are now ~13 years past their randomization to either oCEE or tE2 or placebo, and ~9 years past the termination of study treatment. They are an ideal cohort to investigate potential preventive aspects of mHT as their mHT use was carefully monitored during the clinical trial. Follow-up assessments in the KEEPS Continuation Study will occur at an age (median age=65), when Aβ abnormalities are most likely to dissociate healthy from early AD-related imaging biomarker changes. 19 Thus, participants of the KEEPS Continuation Study are at an ideal age to determine the long-term effects of two different formulations of mHT on preclinical AD pathophysiology. The consequences of AB deposition during early menopausal years are not fully understood, and effectiveness of early mHT for preventing AD-related pathology in the long-term remains unclear. However, reducing Aβ deposition through Aβ-modifying therapies is a widely accepted strategy for preventing AD, and clinical trials are underway in cognitively normal individuals with high AB deposition on PET,² and in APOE ε4 carriers.²⁰ Therefore, the ability to leverage an identified cohort of women who are APOE genotyped, and were exposed soon after menopause to clinically relevant formulations of mHT represents an opportunity not to be missed. Moreover, we are well positioned to investigate the interplay of mHT, cerebrovascular disease, and longitudinal change in cognitive function. A recent examination of records from nearly 500,000 women found that estradiol mHT was associated with lower mortality from vascular dementia (VaD) and AD,21 and the effect was pronounced for VaD, hinting at the underlying mechanisms of cognitive actions. ²¹As discussed in the Funding Opportunity Announcement (FOA), there is a great need to clarify both risk and protective exposures in midlife. Among the FOA research objectives, the KEEPS Continuation most clearly fulfills the proposal's stated goal to 'test whether putative risk or protective factor are truly causal.' Follow-up evaluation of this group of women, whose midlife mHT use and cardiovascular status were well-characterized, provides a singular opportunity to clarify the long-term effects of two formulations of mHT. For women considering mHT, the findings can provide critical insights, guiding their healthcare decisions.

2.3 Estrogens' effects on neurobiology of AD – Importance of the timing of exposure There is compelling evidence that estrogens influence development of AD neuropathology. Estrogens reduce inflammatory responses, ^{22,23} especially to Aβ, ²⁴ improve CSF clearance of insoluble Aβ, ²⁵ while increasing expression of non-toxic soluble Aβ, ²⁶ increase synaptogenesis and dendritic spine density in the hippocampal CA1 field, ^{27,28} and prefrontal cortex, ^{29,30} and exert

antioxidant effects.³¹ In addition, estrogens modulate metabolic function;³² in particular, regulation of brain mitochondrial glucose transport and glycolysis.³³ However, estrogen's effects may depend on the underlying health of the metabolic system. Brinton ^{34,35} proposed the concept of a "healthy-cell bias," which suggests that the health of the neuronal substrate will influence the effects of estrogen exposure. Specifically, estrogens increase mitochondrial respiration and ATP generation in healthy neurons, while protecting cells by improving tolerance for calcium influx and increasing antioxidant actions.³⁶⁻³⁸ In aged or diseased cells, in which calcium homeostasis is disrupted, estrogen-induced calcium influx becomes deleterious to neurons.³⁴ Consistent with this supposition, Espeland et, al, recently reported that women with diabetes (age >65) randomized to oCEE in WHIMS demonstrated twice the risk for dementia,³⁹ and greater gray matter atrophy ⁴⁰ compared to women without diabetes who were assigned to placebo. Importantly, non-diabetic women on oCEE did not show a greater risk for dementia than the reference group. Hence, the risks and benefits of mHT on cognitive function and AD pathophysiology may depend on a woman's age, her overall health, and in particular, her metabolic and vascular health.⁴¹

